## **SYNOPSIS**

# Name of Sponsor/Company:

Vanda Pharmaceuticals Inc.

### Name of Investigational Product:

Tradipitant (VLY-686)

#### **Name of Active Ingredient:**

{2-[1-(3,5-Bistrifluoromethylbenzyl)-5-pyridin-4-yl-1H-[1,2,3]triazol-4-yl]-pyridin-3-yl}-(2-chlorophenyl)-methanone

**Title of Study:** A Multicenter, Randomized, Double-Blind, Placebo-Controlled Study to Assess the Safety and Efficacy of Tradipitant in Treatment-Resistant Pruritus Associated with Atopic Dermatitis

Study center(s): Up to 30 centers in the United States

Indication:	Phase of development:
Chronic pruritus in subjects with atopic dermatitis	П

#### **Number of subjects (planned):**

Approximately 164 subjects randomized (82 per arm, 1:1 randomization scheme)

#### **Inclusion Criteria:**

- 1. Male and non-pregnant, non-lactating female subjects aged 18 65 years (inclusive);
- 2. Diagnosed with atopic dermatitis
  - a. with a SCORAD index  $\leq 80$  at the screening and baseline visits;
  - b. with atopic lesion(s) present at the screening and baseline visits;
- 3. Suffering from chronic pruritus with pruritus being actively present for at least 6 weeks prior to screening despite the use of antihistamines or corticosteroids;
- 4. Average pruritus intensity (VAS) ≥70 mm (during one of the three days preceding the screening and baseline visits);
- 5. Patient assessment of pruritus (VRS (1-5) item "pruritus") ≥3 at screening and baseline visits;
- 6. Subjects with Body Mass Index (BMI) of  $\geq 18$  and  $\leq 35$  kg/m^2 (BMI = weight (kg)/ [height (m)]);
- 7. Subjects must agree to the following study restrictions:
  - a. Males of procreative capacity (not surgically sterile via vasectomy) will use an acceptable method of contraception from randomization through 1 month following the last dose of study medication. Examples of acceptable contraception for males include abstinence, use of a barrier method, or surgically-sterilized or post-menopausal partner.
  - b. Females of child-bearing potential (not surgically sterile or post-menopausal, defined as 12 months without menses) will use an acceptable method of contraception from the earlier of screening or 1 month prior to randomization

through 1 month after the last dose of study medication. Examples of acceptable methods of contraception for females include abstinence, the use of 2 independent barrier methods, or hormonal contraception plus 1 barrier method, or surgically sterilized partner.

- 8. Ability to provide written informed consent;
- 9. Willing and able to comply with all study requirements and restrictions;
- 10. Willing to not participate in any other interventional trial for the duration of their participation;
- 11. Subjects must be in good health as determined by past medical history, physical examination, electrocardiogram, clinical laboratory tests and vital signs.

## **Exclusion Criteria:**

- 1. Chronic pruritus due to condition other than atopic dermatitis (AD)
- 2. Superinfection of AD;
- 3. Unwilling or unable to follow medication restrictions described in Section 7.2, or unwilling or unable to sufficiently washout from use of restricted medication.
- 4. Under medical treatment for a skin disease with a therapy listed in the prohibited medications section that may influence the results of the study; or treatment with Cyclosporin A within the past 6 months.
- 5. Recent history (within six months of screening) of Alcohol Use Disorder or Substance Use Disorder as defined in DSM-5 or a positive drug screen at the Screening visit;
- 6. Subject has ever made a suicide attempt and/or had suicidal ideation of type 4 or 5 on the Columbia Suicide Severity Rating Scale (C-SSRS) or subject is at risk of suicide at Screening or Baseline, in the opinion of the investigator;
- 7. Any medical procedure requiring general anesthetic within three months of the Baseline Visit or any procedure requiring sedation within one month of the baseline visit;
- 8. Current clinically significant cardiovascular, respiratory, neurologic, hepatic, hematopoietic, renal, gastrointestinal or metabolic dysfunction unless currently controlled and stable, including (but not limited to) the following:
  - a. Uncontrolled diabetes mellitus defined as HbA1c >7%;
  - b. Positive hepatitis C antibody test (anti-HCF);
  - c. Positive hepatitis B surface antigen (HBsAg);
- 9. History (including family history) or current evidence of congenital long QT syndrome or known acquired QT interval prolongation;
- 10. Exposure to any investigational medication, including placebo, within 60 days of the Baseline Visit;
- 11. History of intolerance and/or hypersensitivity to medications similar to tradipitant and its accompanying excipients;

- 12. Participation in a previous tradipitant (LY686017 or VLY-686) trial;
- 13. Indication of impaired liver function (including values for AST, ALT, or bilirubin > 1.5 times the Upper Limit of Normal, unless isolated bilirubin > 1.5 x ULN due solely to Gilbert's syndrome);
- 14. Has a creatinine level > 1.25x ULN;
- 15. Anyone affiliated with the site or sponsor and/or anyone who may consent under duress;
- 16. Any other reason as determined by the Investigator which may lead to an unfavorable risk-benefit of study participation, may interfere with study compliance, or may confound study results.

### Investigational product, dosage and mode of administration:

A single oral capsule of tradipitant 85 mg or matching placebo will be orally administered twice daily for a total daily dose of 170 mg. Study medication should be administered with food.

# **Duration of treatment:** 8 weeks

#### **Objectives:**

#### **Primary:**

• To evaluate the efficacy of tradipitant relative to placebo in reducing symptoms of chronic pruritus in subjects with atopic dermatitis

## **Secondary:**

- To evaluate the efficacy of tradipitant relative to placebo in reducing chronic pruritus
- To evaluate the efficacy of tradipitant relative to placebo in reducing atopic dermatitis disease progression
- To evaluate the efficacy of tradipitant relative to placebo in reducing the severity of sleep disruption
- To assess the efficacy of tradipitant on global measures of improvement
- To assess the efficacy of tradipitant on quality of life
- To evaluate the relationship between tradipitant's pharmacokinetics and efficacy measurements
- To explore the safety and tolerability of multiple oral doses of tradipitant.

# **Optional Pharmacogenetic Sub-Study:**

- To identify genetic markers that correlate with response to tradipitant treatment.
- To identify genetic markers that correlate with adverse events that may occur upon treatment with tradipitant.
- To identify genetic markers that are associated with atopic dermatitis and/or pruritus and disorders/diseases associated with NK-1 receptors.
- To identify genetic markers that are associated in the metabolism, distribution, and/or excretion of tradipitant and its metabolites.

## **Overall Design:**

This is a multicenter, randomized, double-blind, placebo-controlled study to be conducted in the United States. Approximately 164 subjects with treatment-resistant pruritus diagnosed with atopic dermatitis, who satisfy the selection criteria for the study, will be randomized to receive either tradipitant 85 mg or matching placebo BID.

The study is divided into two phases: the pre-treatment phase and the evaluation phase. The pre-treatment phase includes a screening and a baseline visit where subjects' eligibility for the study will be assessed. Washout of medications per Section 7.2 will occur during the screening phase. The evaluation phase includes 8 weeks of randomized double-blind treatment. In clinic evaluations will occur at Screening, Baseline, and Weeks 2, 4, 6, and 8.

#### **Criteria for evaluation:**

#### **Efficacy:**

Efficacy assessments will include:

- Daily Diary Itch Scale (DDIS)
- Pruritus Visual Analogue Scale (VAS)
- Verbal Rating Scale (VRS) item "pruritus"
- SCORing Atopic Dermatitis (SCORAD) index
- Eczema Area Scoring Index (EASI)
- Daily Diary Sleep Scale (DDSS)
- Clinical Global Impression of Change (CGI-C)
- Patient Global Impression of Change (PGI-C)
- Skindex-16
- Patient Benefit Index (PBI)

## Safety:

- Safety and tolerability assessments will include the recording of adverse events (AEs), physical examinations, clinical laboratory evaluations, vital signs, and electrocardiograms.
- The Columbia-Suicide Severity Scale (C-SSRS) will be used to assess suicidal behavior and ideation.

#### **Statistical methods:**

## **Primary Endpoint:**

 Mean change from baseline in pruritus symptoms in the tradipitant group versus the placebo group

#### **Secondary Endpoints:**

• Mean change from baseline in pruritus intensity in the tradipitant group versus the placebo group

- Mean change from baseline of disease severity in the tradipitant group versus the placebo group as measured by SCORing Atopic Dermatitis (SCORAD) index
- Mean change from baseline of disease severity in the tradipitant group versus the placebo group as measured by Eczema Area Scoring Index (EASI)
- Mean change from baseline in the daily diary sleep scale(DDSS) in the tradipitant group versus the placebo group.
- Mean global improvement measured by the Clinical Global Impression-Change (CGI-C), Patient Global Impression of Change (PGI-C), Skindex-16, and the Patient Benefit Index (PBI)
- Mean change from baseline in pruritus intensity in relation to serum concentrations of tradipitant and its metabolites.

Statistical analyses will be performed using two-sided tests. The details of analysis models will be specified in the SAP.

**Table 1:** Schedule of Evaluations

Phase	Pre-Treatment		Evaluation				
Visit	V1 Screening	V2 Baseline	V3	V4	V5	V6 EOS or ET	
Study Day	Up to Day -45	Day 0	Day 14 	Day 28 	Day 42 	Day 56  or ET	
Informed Consent Form (ICF) 	X						
Eligibility assessment	X	X					
Subject demography	X						
Medical history	X						
Prior/concomitant medications	X	X	X	X	X	X	
Adverse Event (AE) assessment	$X^3$	X	X	X	X	X	
Serum β-HCG (for WOCBP)	X					X	
Urine pregnancy test (for WOCBP)		X	X	X	X		
HbA1c	X						
Hepatitis B/C screen	X						
Drug and alcohol screen	X	X		X		X	
Hematology, chemistry, and urinalysis	X	X		X		X	
IgE		X					
Pharmacogenetic (PG) sample 		X					
Pharmacokinetic (PK) sample(s)		X	$X^5$	X 	X 	X 	
12-lead resting ECG	X	X	X	X	X	X	
Vital signs and body measurements 	X	X	X	X	X	X	
Physical Examination (PE)	X	X 	$X^8$	X 	X 	X	
C-SSRS 	X	X	X	X	X	X	
Medical History of Pruritus Questionnaire		X					
Pruritus Assessment (incl. VAS, VRS) 	X	X	$X^{11}$	X 	X	X	
SCORing Atopic Dermatitis (SCORAD)	X	X	X	X	X	X	
Eczema Area and Severity Index (EASI)	X	X	X	X	X	X	
Patient Benefit Index (PBI) 		X	X	X	X	X	
Skindex-16		X	X	X	X	X	
Patient Global Impression of Change (PGI-C)			X	X	X	X	
Clinical Global Impression of Change (CGI-C)			X	X	X	X	
Randomization		X					
Study medication dispensation 		X	X	X	X		

Phase	Pre-Treatment		Evaluation			
Visit	V1 Screening	V2 Baseline	V3	V4	V5	V6 EOS or ET
Study Day	Up to Day -45	Day 0	Day 14 	Day 28 	Day 42 	Day 56  or ET
Study medication collection & compliance			X	X	X	X
Subject daily diary distribution and instruction	$X^{15}$					
Subject daily diary review		X	X	X	X	X
Subject daily diary collection						X

EOS = End of Study; ET = Early Termination; WOCBP = Women of Child-bearing Potential; ECG = electrocardiogram; C-SSRS = Columbia Suicide Severity Rating Scale; VAS = Visual Analog Scale; VRS = Verbal Rating Scale

 within +/- 3 days

<sup>2 Informed Consent will be obtained prior to performance of any study procedure(s)

<sup>3 Adverse Event collection will begin at the time the ICF is signed.

<sup>4 The PG blood sample will only be collected for subjects consenting to the PG study.

<sup>5 The PK sample collection should occur within 15 minutes following the pruritus assessment

<sup>6 Multiple PK samples will be collected at V4. In-clinic dosing of study medication (morning dose) will occur at V4 following a pre-dose PK blood draw.

<sup>7 Vital signs will be collected at all visits. Height will be collected at V1(Screening). Body weight will be collected at V1 (Screening), V2 (Baseline), and V6.

<sup>8 An abbreviated physical examination may be performed at V2 (Baseline), V3, V4, and V5 if clinically indicated.

<sup>9 The Screening/Baseline C-SSRS will occur at V1 (Screening). The Since Last Visit C-SSRS will occur at all other visits.

<sup>10The baseline pruritus assessment will be completed at V1 and V2. The post-baseline pruritus assessment will be completed at V3, V4, V5, and V6.

<sup>11At V3, V5, and V6, the Pruritus Assessment will be conducted between 2 and 4 hours post study drug administration

<sup>12At V4, the Pruritus assessment will occur at 03:00 (+/- 00:30) post in-clinic study drug administration

<sup>13At V2 (Baseline), The Patient Needs Questionnaire (PBI-PNQ) will be administered. The Patient Benefits Ouestionnaire (PBI-PBQ) will be administered at subsequent visits.

<sup>14Subjects will be instructed to take their first dose of study medication on the evening of Day 0.

<sup>15The subject diary will be completed for at least 7 days prior to randomization and the duration of the evaluation phase.

1. STATISTICS

1.1. Sample Size and Accrual

The sample size chosen for this study is not based on statistical considerations. This sample size was chosen after taking into consideration historical data Approximately 164 patients will be randomized.

1.2. Statistical Methods and Analysis Plan

This section describes the planned statistical analyses in general terms. A complete description of the methodology will be specified in a statistical analysis plan (SAP). Any changes in the statistical methods described in this protocol that occur prior to database lock will be documented in the SAP and will not require a protocol amendment.

1.2.1. General

Statistical analyses will be performed using two-sided tests.

Data will be summarized by treatment group (and by visit when applicable), with respect to demographic and baseline characteristics, efficacy variables, and safety variables.

Summary statistics will include the mean, N, standard deviation, median, minimum, and maximum values for continuous variables, and frequencies and percentages for categorical variables.

For the analyses of change from baseline, only subjects with a baseline and at least one (1) post-baseline measure will be included in the analysis. Unless otherwise specified, baseline is defined as the latest non-missing observation across all the visits in the screening phase, before the active study drug begins. Endpoint will be the latest non-missing observation across all the post-baseline visits in the evaluation phase.

Low enrolling sites will be pooled for analysis and the pooling algorithm will be determined prior to breaking the blind. The goal of pooling low enrolling sites is to have a sufficient number of subjects per treatment group within a site for the analysis models and for the evaluation of the treatment-by-site interaction for the primary endpoint. Unless otherwise specified, the pooled sites will only be used in the analyses where site has an effect. The actual sites rather than the pooled sites will be specified in data listings.

VP-VLY-686-2102 Protocol

Details of the model and the analyses will be specified in the SAP. All statistical analyses will be performed using SAS®, Version 9.1.3 or higher.

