1.2.2. Subject Populations for Analysis

The following analysis populations will be defined for this study:

Intent-to-Treat: will include any subject randomized into the study that receives a dose of study drug and that has completed at least one post-baseline efficacy measurement while on study medication;

Safety: Any subject randomized into the study that receives a dose of study drug;

Per-Protocol: Any subject who is randomized and receives the protocol required study drug exposure and required protocol processing.

Efficacy analyses will be performed on the Intent-to-Treat population and the Per-Protocol population. Safety summaries will be based on Safety set. Subject characteristics will be presented for all subjects randomized.

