1.3. Efficacy Data Analysis

1.3.1. Primary Outcome and Methodology

The primary efficacy outcome measure for the double-blind phase will be the mean change from baseline in pruritus symptoms. A detailed description of the primary analysis model will be included in the SAP.

As stated previously, any changes in the statistical methods that occur prior to database lock will be documented in the SAP and will not require a protocol amendment.

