1.3.2. Secondary Efficacy Analysis

The secondary efficacy outcomes include:

- DDSS
- Itch questionnaires including VAS, VRS, DDIS
- SCORAD index;

- Objective SCORAD;
- EASI:
- PGI-C;
- CGI-C;
- PBI;
- Skindex-16;
- Pharmacokinetic-Pharmacodynamic correlation.

Continuous endpoints will be summarized and analyzed in a manner similar to the primary endpoint. Details of the analysis will be described in the SAP.

Categorical variables will be evaluated as described in the SAP. Time to event data will be analyzed using the Kaplan-Meier method, and the treatment group differences will be tested by the log-rank test. Details of the analysis will be described in the SAP.

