1.4.1. Adverse Events

Adverse events will be recorded throughout the study and at early discontinuation. Adverse events and medical conditions will be coded using the Medical Dictionary for Regulatory Activities (MedDRA) coding dictionary. Treatment-emergent adverse events will be defined as those events, which are newly occurring or worsening from baseline. In all cases only treatment emergent adverse events will be summarized.

Treatment-emergent adverse events will be summarized within each treatment group by primary system organ class and preferred term. (*NOTE*: In any given category [e.g. body system] a subject will only be counted once.) The incidence rates of TEAEs will be analyzed as described in the SAP. Similar displays will be provided for SAE and prior (conditions ending prior to the first dose of study medication and current (conditions present while on study medication) medical conditions.

Adverse events will further be categorized by severity, relationship to study medication, and action taken. Other information collected will be listed, as appropriate. Any event starting more than 3 days after the final dose of study medication will be excluded from the above tables and only listed, unless the event caused discontinuation.

The proportions of subjects experiencing SAEs and AEs resulting in discontinuation from the study will be summarized by treatment groups.

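### The only stated rule for choosing a post-baseline value is last observation carried forward, and the plan does not say which efficacy tests use it

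*SAP*

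**What the plan says.** SAP 1.2.1 (General) has one paragraph on change-from-baseline analyses. It restricts them: "only subjects with a baseline and at least one (1) post-baseline measure will be included in the analysis". It defines baseline and then the post-baseline value: "Endpoint will be the latest non-missing observation across all the post-baseline visits in the evaluation phase". The term Endpoint in this sense does not appear again.

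The primary outcome in the protocol synopsis is "Mean change from baseline in pruritus symptoms in the tradipitant group versus the placebo group", with no time point. SAP 1.3.1 repeats it and defers the rest: "A detailed description of the primary analysis model will be included in the SAP". SAP 1.2 likewise leaves the full methodology to a further plan. Other continuous outcomes follow the primary (SAP 1.3.2): "Continuous endpoints will be summarized and analyzed in a manner similar to the primary endpoint".

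On time and treatment, the synopsis says "The evaluation phase includes 8 weeks of randomized double-blind treatment". Table 1 puts early termination in the same V6 column as Day 56 and gives a window of ±3 days for V3 to V6. Footnote 11 of Table 1 times the V6 pruritus assessment at 2 to 4 hours after study drug. SAP 1.2.2 admits a subject to the Intent-to-Treat set if the subject "has completed at least one post-baseline efficacy measurement while on study medication". That decides who is analysed, not which value is used.

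**The concern.** The primary outcome is a change from baseline, and the paragraph on such analyses offers one way to pick the later value. A statistician programming from this text would probably use it. A value from Week 2, 4 or 6, or from an early-termination visit, would then stand in for Week 8.

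That is harmless only in special cases. If symptoms are still improving, a leaver's value understates the eventual improvement, so the arm that loses more subjects looks worse. If the treatment difference is still growing, early values shrink it even with equal dropout. If subjects leave because they itch, the carried values are also selected. SAP 1.2.3 plans to compare the arms on time to discontinuation for adverse events, lack of efficacy and any reason, so the plan itself treats such dropout as worth examining.

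The continuous secondary outcomes would inherit whatever the primary test does.

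**Working it through.** **1. What can be reproduced.** Only 2 × 82 = 164. SAP 1.1 says the sample size has no statistical basis, and the documents give no alpha, SD, effect, dropout rate or time course, and do not name the primary scale. Everything below is illustrative.

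**2. Hand check.** Assume dropout unrelated to outcome, with leavers' last values spread evenly over Weeks 2, 4 and 6. In each arm:

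Endpoint mean = (1 − d) × Week 8 mean + d × average of the Week 2, 4 and 6 means.

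Assumed placebo improvement is 15, 22, 26, 28 mm. The early average is 63/3 = 21, so a leaver loses 28 − 21 = 7 mm.

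- *No true difference, same course:* false benefit = 7 × (d placebo − d drug). Equal dropout gives 0. Drug 15%, placebo 24%: 7 × 0.09 = 0.6 mm. Drug 25%, placebo 10%: 1.05 mm against drug.
- *True 10 mm at Week 8* (drug 18, 28, 35, 38; early average 81/3 = 27; loss 11 mm): estimate = 10 − 11 × d drug + 7 × d placebo. Drug 30%, placebo 17%: 10 − 3.30 + 1.19 = 7.9 mm. Both 20%: 10 − 2.2 + 1.4 = 9.2 mm. Drug 10%, placebo 30%: 10 − 1.1 + 2.1 = 11.0 mm.
- *Equal at Week 8 but faster on drug* (23, 27, 28, 28; loss 2 mm): with 20% in both arms, 7 × 0.20 − 2 × 0.20 = 1.0 mm in favour of drug.

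For scale, with SD 25 the standard error of a difference is 25 × √(2/82) = 3.9 mm.

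**3. Simulation with outcome-related dropout.** Assumptions:

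- 82 per arm, two-sided 5%, baseline SD 9, slope of change on baseline −0.5, SD of change 25, residual correlation 0.6.
- Improvement of 30 mm (40 mm on drug where an effect is assumed), with 40/65/85/100% of it reached at Days 14/28/42/56.
- Dropout after Days 14, 28 and 42, at 1 log-odds per SD of the last value.
- Early-termination values on treatment course, on a day uniform between visits.
- The target is the Week 8 difference had all stayed on treatment.

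Endpoint is analysed by covariance analysis. The three Endpoint figures are for all / half / none of the leavers giving an early-termination value.

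| True effect; dropout drug vs placebo | Endpoint difference (mm) | Rejection rate, Endpoint (%) | Mixed model (mm) |
|---|---|---|---|
| 0; 15 vs 19% | 0.3 / 0.6 / 0.8 | 5.0 / 5.3 / 5.8 | below 0.1 |
| 0; 15 vs 24% | 0.8 / 1.3 / 1.8 | 5.5 / 6.1 / 7.4 | below 0.1 |
| 0; equal, same course | within 0.1 | about 5 | about 0 |
| 10; 30 vs 17% | 7.9 / 7.1 / 6.3 | 48 / 37 / 29 | 9.9–10.0 (power 65%) |
| 10; about 20% each | 9.3 / 9.2 / 9.1 | 63 / 58 / 55 | 10.0 (power 67–68%) |
| 10; 15 vs 24% | 10.3 / 10.7 / 11.1 | not tabulated | 10.0 |

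Repeat runs moved the Endpoint figures by about 0.3 mm at most. For example, the 15 vs 24% null case reached 2.0 mm with no early-termination values, and the 30 vs 17% case ranged over 7.6–8.0 mm with all and 6.1–6.6 mm with none. The mixed model stayed within 0.2 mm of the truth.

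**4. When dropout depends on the next, unseen value.** With no true difference and 15% vs 25%, Endpoint errs by 0.7–0.9 mm for drug and the mixed model by 0.6–0.7 mm against it. Neither is clearly better.

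**5. Visit windows.** Days 14, 28, 42 and 56, each ±3, cover Days 11–17, 25–31, 39–45 and 53–59. Days 1–10, 18–24, 32–38 and 46–52 match no visit. Endpoint needs no window, but a by-visit model does. Of the 14 days after a completed visit, only the last 4 fall in the window of the next, empty visit: 4/14 = 29% of early-termination values would enter and 71% would not. The simulation has no leavers before Day 14, so it does not test Days 1–10.

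**The case against.** *The model is expressly deferred.* The statistics text describes itself as general and promises a further plan, which may already name a model and time point. This stands. It makes the bias conditional, but the text still contains a rule whose scope is undefined.

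*Other analyses give context.* Efficacy is also summarized by visit where applicable, a Per-Protocol analysis is planned, and discontinuation is compared between arms. These would help reveal a problem, but none says which value enters the primary test.

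*The effect is small if the schedule is followed.* Table 1 provides an early-termination visit, so the first figure in each triplet fits the plan best. There the null error rate is 5.0–5.5% in the two cases shown. This stands for false positives. The loss of effect and power at 30% vs 17% remains material.

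*The mixed model is not assumption-free.* It assumes data missing at random and, as step 4 shows, can err about as much as Endpoint when that fails. This stands, and is why a further sensitivity analysis is needed.

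*Off-drug values.* A reader might infer that Endpoint would routinely pick up off-drug itch scores, because it has no on-drug condition. Footnote 11 does not support this for the VAS and VRS, since it schedules the V6 assessment after a dose. The possibility is left mainly for SCORAD, EASI and other measures without that timing, and is secondary. Nor does the 3-day limit in SAP 1.4.1 show an inconsistency: it is a rule for adverse-event tables.

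**Conclusion.** The point holds in conditional form. The plan states one rule for choosing a post-baseline value, it works as last observation carried forward for leavers, and its use is not assigned to any test. A reader might conclude that the primary analysis is last observation carried forward and its result therefore biased. The documents do not go that far: no passage ties Endpoint to the primary test.

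If it is used, the error can favour or penalize the drug. Under the stated assumptions it is about 0.8 mm to 2 mm of false benefit at 15% vs 24% dropout. At 30% vs 17%, a true 10 mm is reduced to about 8 mm, or about 6 mm without early-termination values. It is near zero with no true difference, equal dropout and the same course. These sizes depend on an assumed SD, time course, dropout pattern and on-treatment Week 8 target. Confidence is medium. This is a cheap improvement, not a fatal flaw.

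**What to change.** Add to SAP 1.2.1 wording to this effect:

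- Efficacy change-from-baseline analyses use a likelihood-based mixed model for repeated measures on Weeks 2, 4, 6 and 8 (or the matching diary periods), with treatment, visit, treatment-by-visit, baseline and baseline-by-visit terms and an unstructured covariance. Week 8 is the primary contrast.
- Endpoint is used only for a last-observation sensitivity analysis and for safety summaries.
- An early-termination value enters the model only if taken within ±3 days of a scheduled visit that has no value. It is never labelled Week 8 merely because it shares the V6 column. Values on Days 1–10, 18–24, 32–38 or 46–52 go to the Endpoint sensitivity analysis.
- The number of subjects who meet the inclusion rules of 1.2.1 and 1.2.2 but have no value in the model is reported by arm. A leaver whose only value falls on Days 1–10 is such a case.
- One sensitivity analysis assumes data not missing at random, for example placebo-based imputation.

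If a separate SAP already fixes the model, refer to it here and still state where Endpoint is used.

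The cost is wording and a little programming, with no new data. SAP 1.2 allows method changes before database lock to be recorded in the SAP without a protocol amendment. The downside is that the primary model rests on missing at random and leaves out most off-schedule early-termination values (about 71% if their day is uniform between visits).
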